#### **Statistical Analyses for Efficacy**

All efficacy endpoints will be analyzed on the ITT population. In addition, the primary efficacy endpoints will be analyzed in the Per-Protocol Population, if defined.

No missing data imputation will be applied, and all assessments prior to premature discontinuation from study drug will be used.

Statistical Analyses for Safety – how will data be summarized? % of patients with AEs? The safety analyses will be carried out using the Safety Population. % of patients with AE's will be assessed inclusive of physical examination, laboratory assessments, and vital sign abnormalities.

Note that missing safety data will not be imputed.

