## PROTOCOL SYNOPSIS

Study Title	A 24 Week, Open-Label Study to Evaluate the Efficacy and Safety of Upadacitinib in Patients with Moderate-to-Severe Prurigo Nodularis
Sponsors	[name]
Study Objectives	
Primary Objective: To explore the effectiveness of upadacitinib in patients with prurigo nodularis.
 
Secondary Objectives: To explore the safety of upadacitinib in patients with prurigo nodularis.

Study Design	A single center, open-label study of 25 subjects to assess 24 weeks upadacitinib in patients with moderate-to-severe prurigo nodularis.
Study Centers	Eczema Treatment Center of New Jersey [name]
Study Population	25 adult male and female subjects with moderate-to-severe prurigo nodularis
Main Inclusion Criteria	
 
1. Male or female adult 18-64 years of age at time of screening.
 
2. Diagnosis of prurigo nodularis for <math>\geq</math> 3 months.
 
3. Moderate-to-Severe prurigo nodularis as determined by at least 10 PN lesions on legs and/or arms and/or trunk at screening and baseline .
 
4. Failure of at least a 2-week course of medium to super potent TCS or TCS is not medically advisable for subject.
 
5. Females of childbearing potential must not have a positive serum pregnancy test at the Screening Visit and must have a negative urine pregnancy test at the Baseline Visit prior to study drug dosing. Note: subjects with borderline pregnancy test at Screening must have a serum pregnancy test <math>\geq</math> 3 days later to determine eligibility. If female, subject must be postmenopausal OR permanently surgically sterile OR for females of childbearing potential practicing at least one protocol specified method of birth control, that is effective from the Baseline Visit through at least 30 days after the last dose of study drug. Female subject must not be pregnant, breastfeeding or considering becoming pregnant during the study or for approximately 30 days after the last dose of the study drug.
 
6. Subject is a candidate for systemic therapy per investigator discretion.
 
7. Able and willing to give written informed consent prior to performance of any study-related procedures.
 
8. Subject must be in general good health as judged by the Investigator, based on medical history, physical examination.
 

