Study Endpoints	Primary Endpoint: Proportion of participants with improvement (reduction) in worst-itch numeric rating scale (WI-NRS) by $\geq 4$ from baseline to Week 12. [Time Frame: Baseline to Week 12 ]WI-NRS is a patient-reported outcome (PRO) comprised of a single item rated on a scale from 0 ("No itch") to 10 ("Worst imaginable itch). Secondary Endpoints: Proportion of patients with improvement in worst-itch numeric rating scale (WI-NRS) by $\geq 4$ from baseline to Week 24 IGA PN-S 0 or 1 at weeks 12 & 24 IGA PN-A 0 or 1 at week 12 & 24 Percent improvement of PN-S & PN-A at week 12 & 24 DLQI improvement at weeks 12 & 24 Adverse Events
References	Tessa B. Mullins, Poonam Sharma, Christopher A. Riley, Sidharth Sonthalia. Prurigo Nodularis. StatPearls [Internet]. Treasure Island (FL): StatPearls Publishing; 2021 Jan. 2020 Sep 15.  Eric H Kowalski, Diana Kneiber, Manuel Valdebran, Umangi Patel, Kyle T Amber. Treatment-resistant prurigo nodularis: challenges and solutions. Clin Cosmet Investig Dermatol. 2019 Feb 28;12:163-172. doi: 10.2147/CCID.S188070. eCollection 2019.

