## **8.2 Statistics**

It is desired to enroll 25 patients.

Primary Endpoint: Proportion of participants with improvement (reduction) in worst-itch numeric rating scale (WI-NRS) by  $\geq 4$  from baseline to Week 16 [Time Frame: Baseline to Week 12] WI-NRS is a patient-reported outcome (PRO) comprised of a single item rated on a scale from 0 ("No itch") to 10 ("Worst imaginable itch").

Secondary Endpoints: Percent improvement (reduction) in worst-itch numeric rating scale (WI-NRS) by  $\geq 4$  from baseline to Week 24

IGA PN-S 0 or 1 at weeks 12 & 24

IGA PN-A 0 or 1 at week 12 & 24

Percent improvement of PN-S & PN-A at week 12 & 24

DLQI improvement at weeks 12 & 24

Adverse Events

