### **8.2.1 Additional Statistical Considerations**

The objective of the statistical analyses is to assess the efficacy and safety of upadacitinib for the treatment of subjects with moderate to severe PN who are candidates for systemic therapy. The Primary Analysis for all efficacy endpoints will be conducted after all continuing subjects have completed the study activities up to Week 16. The Intent-to-Treat (ITT) Population consists of all randomized subjects and will be used for the efficacy analyses. A Per-Protocol Population may be defined if deemed necessary to exclude subjects with major protocol violations. The criteria to define the Per-protocol Population will be detailed in the SAP. Subjects to be excluded from the Per-Protocol Population will be finalized before week 16. The Per-Protocol Population, if defined, will be used to analyze the primary efficacy endpoint.

The Safety Population consists of all randomized subjects who received at least 1 dose of study drug. An All Upadacitinib Treated Population consists of all subjects who received at least one dose of upadacitinib in the study. This population will be used to provide a comprehensive summary of safety.

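### Itch efficacy is planned as a 4-point responder proportion with no interval, and no analysis of WI-NRS change on its own scale is named

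*Combined protocol and SAP*

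**What the plan says.** The synopsis describes the study as "A single center, open-label study of 25 subjects to assess 24 weeks upadacitinib", with the primary objective "To explore the effectiveness of upadacitinib in patients with prurigo nodularis". Section 8.2.1 words the aim more firmly: "The objective of the statistical analyses is to assess the efficacy and safety of upadacitinib". On size, section 8.2 says only "It is desired to enroll 25 patients".

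The synopsis gives the primary endpoint as "Proportion of participants with improvement (reduction) in worst-itch numeric rating scale (WI-NRS) by" at least 4 points at Week 12, and a secondary endpoint as "Proportion of patients with improvement in worst-itch numeric rating scale (WI-NRS) by" the same amount at Week 24. Section 8.2 words the primary endpoint as "from baseline to Week 16 [Time Frame: Baseline to Week 12". It also calls the Week 24 itch endpoint a percent improvement while keeping the 4-point cut. Section 6 attaches Week 16 to the primary endpoint, and section 8.2.1 times the primary analysis at Week 16.

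On method, the efficacy section says "All efficacy endpoints will be analyzed on the ITT population". It allows an optional per-protocol analysis, rules out imputation, and says that assessments before discontinuation of study drug will be used. Section 8.2.1 defines the ITT population as the randomised subjects. The only item it leaves to a SAP is the per-protocol criteria.

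The schedule of events (section 8.3) has patient-reported outcomes at baseline and at Weeks 4, 8, 12, 16, 20 and 24.

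**The concern.** A single-arm percentage from 25 people is read at face value unless its uncertainty is printed beside it, and nothing in section 8.2 or 8.2.1 requires that. The repeated 0-to-10 scores, already scheduled, would show the size and time course of the itch change, but no analysis of them is named.

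The cut also loses information on individuals. Someone who improves by 3 points counts the same as someone who does not improve. Section 5.2.1 sets no minimum baseline WI-NRS, so a subject who enters below 4 cannot be a responder however much the itch improves.

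At stake is how much the study can say about its main question. It has no control arm, so clear estimates with stated precision are most of what it can deliver.

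**Working it through.** **The plan's own figure.** The 25 cannot be reproduced: no alpha, power, expected rate, reference rate, SD or target width is given.

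**Which itch visits have a role.**

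| Visit | Stated role of the itch score |
|---|---|
| Baseline | Reference for change |
| Weeks 4, 20 | None |
| Week 8 | Dose adjustment only (section 5.5.1.3) |
| Week 12 | Primary in the synopsis; time frame in section 8.2 |
| Week 16 | Primary in the text of section 8.2; also sections 6 and 8.2.1 |
| Week 24 | Secondary |

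**Precision of a proportion.** The input is n = 25 (section 8.2). The Clopper-Pearson limits for x responders are: lower = 2.5% quantile of Beta(x, n − x + 1); upper = 97.5% quantile of Beta(x + 1, n − x).

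| Responders | Rate | Exact 95% interval | Width (points) |
|---|---|---|---|
| 5/25 | 20% | 6.8% to 40.7% | 33.9 |
| 10/25 | 40% | 21.1% to 61.3% | 40.2 |
| 13/25 | 52% | 31.3% to 72.2% | 40.9 |
| 15/25 | 60% | 38.7% to 78.9% | 40.2 |
| 20/25 | 80% | 59.3% to 93.2% | 33.9 |

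**Effect of the denominator.** Nobody is randomised, so the ITT definition does not fix the denominator, and without imputation it could fall below 25. Assume 10 responders and 5 subjects with no score at the primary week. Then 10/20 is 50% (27.2% to 72.8%), while 10/25 is 40% (21.1% to 61.3%).

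**Information kept by the cut.** Assume a normally distributed change with known SD. With response rate P and c the normal quantile of P, the yes/no outcome carries a fraction φ(c)² / [P(1 − P)] of the information on the mean.
- P = 0.5: 0.3989² / 0.25 = 0.637.
- P = 0.3 or 0.7: 0.576.
- P = 0.2 or 0.8: 0.2800² / 0.16 = 0.490.

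On that model, 25 subjects analysed on the scale are worth 25/0.637 = 39 to 25/0.490 = 51 dichotomised subjects for estimating the mean, before any gain from the other visits.

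**Precision of a mean change.** The half-width is t(0.975; 24 df) × SD / √25 = 2.064 × SD / 5. For assumed SDs of 2, 2.5 and 3 points this is 0.83, 1.03 and 1.24 points.

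**If a benchmark were used.** The smallest count with a one-sided exact tail of at most 0.025 is 10/25 against an assumed 20% (tail 0.0173) and 13/25 against an assumed 30% (tail 0.0175). The documents give neither rate.

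**The case against.** The strongest reply is that the study sets out to explore, states no hypothesis and makes no success claim, so a descriptive proportion may be enough. That stands as far as a benchmark goes: naming one is a choice, not a requirement. It does not remove the need for an interval, since an exploratory estimate without its precision is hard to use.

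A second reply is that the information-loss figure depends on a normal model with known SD, whereas WI-NRS is a bounded single item and the planned target is a proportion. That also stands. The figure is indicative, and adding a mean-change analysis does not make the responder proportion itself more precise.

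Third, a repeated-measures model can be too large for the data. An unstructured covariance over six post-baseline visits has 6 × 7 / 2 = 21 parameters, from 25 subjects. The model therefore needs a pre-stated fallback.

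Three stronger readings are tempting but not supported:
- **That Week 16 itch goes unused.** Sections 6, 8.2 and 8.2.1 all attach Week 16 to the primary endpoint or analysis.
- **That every efficacy endpoint is a raw proportion.** Percent improvement in the two IGA scales and DLQI improvement are not worded that way, and the Week 24 itch wording in section 8.2 is ambiguous. The general sentence on using assessments before discontinuation does not exclude intermediate scores either, although it names no analysis for them.
- **That any percentage of 25 could be declared efficacy.** No threshold is set, but no such declaration is planned.

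**Conclusion.** The point holds as a cheap improvement. The plan gives no interval for the itch response, names no analysis of WI-NRS change on its scale, and leaves the primary week in conflict between Week 12 and Week 16.

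The interval widths of about 34 to 41 points follow exactly from n = 25 for observed rates of 20% to 80%; fewer evaluable subjects would widen them. The 49% to 64% efficiency rests on an assumed normal change, and the half-widths of 0.83 to 1.24 points rest on assumed SDs.

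None of this makes the responder endpoint wrong. A reader might go further and conclude that the study cannot inform on efficacy without a reference rate. The documents do not support that, because the stated purpose is exploratory and an uncontrolled response rate with its interval is a legitimate result.

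**What to change.** 1. Reconcile the primary week across the synopsis and sections 6, 8.2 and 8.2.1. Keep the 4-point responder endpoint at that week, and word the Week 24 itch endpoint the same way in both lists.
2. Report each proportion with a two-sided 95% Clopper-Pearson interval. Define the denominator as all treated subjects, in place of all randomised. State that a subject with no score at the visit then counts as not having responded, reconcile this with the no-imputation sentence, and show the observed-case proportion beside it.
3. Add a supporting repeated-measures model of WI-NRS change at Weeks 4 to 24, with visit and baseline score as terms. Report the mean change and 95% interval at the reconciled primary week and at Week 24. Use the same model for DLQI, which also gives DLQI improvement a defined meaning. State that the model uses the available on-drug scores without imputation and assumes data missing at random.
4. Pre-state a simpler covariance structure, such as first-order autoregressive or compound symmetry, for use if the unstructured model does not converge.
5. Describe results after Week 8 as those of the response-adjusted regimen, because dose then depends on the itch response.
6. Describe the main result as an uncontrolled response rate. A benchmark is optional; if one is used, name it before the first analysis.

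The cost is some protocol and SAP wording and a little more analysis of data already scheduled. The reported precision will look modest.

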#### **5.5.1.3 Upadacitinib Dosage Adjustments**

Upadacitinib will be dispensed and administered as 15mg QD at baseline. For subjects who do not achieve  $\leq$  2-point reduction in itch at week 8, upadacitinib dosage will be increased to 30mg QD. The investigator may reduce the dose to 15mg QD after week 16 per investigator discretion. If an SAE or an adverse event that is thought to be related to study drug and is not alleviated by symptomatic intervention, study drug will be discontinued. Subjects who permanently discontinue study drug under this protocol should receive standard care of prurigo nodularis treatment as prescribed by their physician.

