### **5.6.8 Early Discontinuation Procedures**

Subjects will be prematurely discontinued from the study under the following conditions:

1. Subject requests to withdraw from the study.
2. Subject experiences an adverse event that makes it difficult or intolerable for the subject to continue treatment, or increases risk to the subject, or interferes with the investigator's ability to clinically evaluate the progress of the subject's treatment.
3. Subject begins an unapproved concomitant therapy for prurigo nodularis, atopic dermatitis or another medical condition that may increase risk to the subject if continuing study treatment.
4. Subject cannot be reached / lost to follow-up.
5. The study investigator suspends or terminates the study.
6. Other unanticipated reason.

Any subject who prematurely discontinues the study should complete the week 24 (End of Study) assessments.

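### The no-imputation rule leaves the denominator of the primary responder rate unstated, and its natural reading turns an ITT analysis into an observed-case rate

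*Combined protocol and SAP*

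**What the plan says.** The primary endpoint in the synopsis begins "Proportion of participants with improvement (reduction) in worst-itch numeric rating scale (WI-NRS" and requires a fall of at least 4 points from baseline at one visit. It is therefore a binary outcome reported as a proportion. The secondary endpoints include the same response at Week 24 and IGA PN-S and PN-A scores of 0 or 1 at Weeks 12 and 24.

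Under Statistical Analyses for Efficacy in section 8.2.1, the plan states "All efficacy endpoints will be analyzed on the ITT population" and gives one missing-data rule: "No missing data imputation will be applied, and all assessments prior to premature discontinuation from study drug will be used".

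Three other places bear on the denominator:

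- Section 8.2.1 defines ITT by randomization, although the study has one open-label arm. It also defines a set that would fit, "An All Upadacitinib Treated Population consists of all subjects who received at least one dose of upadacitinib in the study", but assigns it to safety.
- The only matter that section 8.2.1 defers to a separate plan is the optional Per-Protocol set: "The criteria to define the Per-protocol Population will be detailed in the SAP". That set deals with protocol violations, not missing scores.
- Section 5.6.8 asks early leavers for the Week 24 assessments but does not say which analysis visit those values belong to.

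The documents describe no missing-data sensitivity analysis.

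**The concern.** A subject with no score at the primary visit cannot be called a responder or a non-responder without a rule. Calling that subject a non-responder is usually regarded as imputation, which the plan rules out. The natural result is that the subject leaves the denominator. Because the rule names only scores obtained before study drug is stopped, a subject who stops drug but still attends may also have no usable score.

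Such cases are foreseeable. Section 5.5.1.3 provides that, for certain adverse events where the problem "is not alleviated by symptomatic intervention, study drug will be discontinued". Section 5.6.8 lists withdrawal, adverse events that make continuing intolerable, starting an unapproved therapy for prurigo nodularis, and "Subject cannot be reached / lost to follow-up". Some of these reasons are plausibly linked to a poor result on treatment. If missing subjects respond less often than observed ones, the observed-case rate is too high.

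With no control arm and no test, the response proportion is the main efficacy result. Two analysts following the same text could report different values for it, and in an open-label study the choice could be made after the data are seen.

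**Working it through.** The plan has no figure to reproduce. Section 8.2 says only "It is desired to enroll 25 patients", with no expected response rate, dropout rate, power or test.

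**Inputs.** N = 25 (section 8.2), assuming that all 25 are enrolled and dosed. The number of observed responders r and the number without a usable primary-visit score m are assumptions.

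**Two readings of the same data.**

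- Observed-case: r/(25 − m)
- Missing counted as non-response: r/25
- Ratio of the first to the second: 25/(25 − m), which is 1.00, 1.04, 1.09, 1.14, 1.19 and 1.25 for m = 0 to 5

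The gap, r/(25 − m) − r/25, in percentage points:

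| r | m = 1 | m = 3 | m = 5 |
|---|---|---|---|
| 0 | 0 | 0 | 0 |
| 6 | 1.0 | 3.3 | 6.0 |
| 12 | 2.0 | 6.5 | 12.0 |
| 18 | 3.0 | 9.8 | 18.0 |

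The gap is zero if m = 0 or if nobody responds.

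**Rates for r = 12, with exact (Clopper-Pearson) 95% intervals.** Missing as non-response gives 12/25 = 48.0% (27.8 to 68.7) whatever m is. The best case counts every missing subject as a responder, (12 + m)/25.

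| m | Observed-case | Best case |
|---|---|---|
| 1 | 12/24 = 50.0% (29.1 to 70.9) | 13/25 = 52.0% (31.3 to 72.2) |
| 3 | 12/22 = 54.5% (32.2 to 75.6) | 15/25 = 60.0% (38.7 to 78.9) |
| 5 | 12/20 = 60.0% (36.1 to 80.9) | 17/25 = 68.0% (46.5 to 85.1) |

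**Error against the true rate.** Let k of the m missing subjects be ones who would have responded, so the true rate is (12 + k)/25.

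- Observed-case error: 12/(25 − m) − (12 + k)/25. As k goes from 0 to m, it runs from +2.0 to −2.0 points at m = 1, from +6.5 to −5.5 at m = 3, and from +12.0 to −8.0 at m = 5. It is zero at k = 12m/(25 − m), that is 0.5, 1.64 and 3.0.
- Non-response error: 12/25 − (12 + k)/25 = −4k points. It runs from 0 to −4, 0 to −12 and 0 to −20 for m = 1, 3 and 5.

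**The case against.** The strongest reply is that the remedy is a preference. On the figures above, missing-as-non-response has the larger worst-case error (−20 points against +12.0 at m = 5) and can err only downward. The arithmetic stands, and it is why the observed-case and best-case rates should be reported alongside. It does not rescue the present text, which commits to no denominator. Counting missing as non-response keeps every treated subject in the analysis, and its error has a known sign and bound.

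A reader might infer that the plan's rate is biased upward. The documents do not support that. Observed-case can never be below missing-as-non-response, because r/(25 − m) is at least r/25. That is an identity between two rules, not evidence of bias. The reasons for discontinuation make lower response among missing subjects plausible, but give no data on it.

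A reader might also infer that the result could not be compared with other prurigo nodularis trials. The documents mention such trials but give neither their response rates nor their missing-data rules, so that argument is not made here.

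It is also true that the magnitude is wholly assumed, and that the gap at m = 1 or 3 is small beside an interval about 41 points wide (68.7 − 27.8). The 18-point gap needs 5 missing and 18 of 20 observed subjects responding.

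**Conclusion.** The point holds as a gap in the primary analysis that is cheap to close. The plan does not state the denominator, and its natural reading is observed-case under an ITT label. Responders over all ITT subjects is not excluded, so it would be too strong to say that the plan expressly specifies an observed-case analysis.

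With 12 assumed responders, the choice of reading moves the reported rate by 2.0, 6.5 or 12.0 points with 1, 3 or 5 missing. These sizes rest on 25 treated subjects and on assumed values of r and m. The direction of any bias against the true rate is not established. The trial is exploratory and sets no test or threshold, so the consequence is for the size of the reported rate, not for a stated decision.

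**What to change.** For the WI-NRS and IGA 0/1 responder endpoints, replace the no-imputation sentence in section 8.2.1 with wording such as: *the denominator is every subject dosed at least once; a subject with no usable score at the visit is counted as a non-responder*. The old sentence cannot remain for these endpoints, because it contradicts the new rule. In the efficacy set definition, replace randomized subjects with treated subjects.

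Report the number missing at each visit. Give the observed-case and best-case rates with exact intervals as sensitivity analyses. In a single arm the worst case is already the headline rate.

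Three further statements are needed for the rule to work:

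- whether scores observed after study drug is stopped count;
- that assessments done at early termination are labelled by their actual timing, not as Week 24;
- which week is primary, since that determines who is missing. The synopsis says Week 12, section 8.2 gives both Week 16 and Week 12, and section 8.2.1 times the primary analysis at Week 16.

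Missing data for percent PN-S and PN-A improvement and for DLQI improvement are a separate matter.

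The cost is wording only. Section 8.3 already schedules the questionnaires and efficacy assessments at every visit from baseline to Week 24. The downside is a conservative headline rate. With 12 responders it understates response by at most 4, 12 and 20 points with 1, 3 and 5 missing, and only if every missing subject would have responded.
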